	08/05/2015	
a complete response to the FDA's deficiency request:
 
 • Synopsis, section 5.2, appendix 1 – exclude patients unwilling or unable to stop supplemental sex hormone therapy (estrogen, progesterone, and/or testosterone preparations) • Schema, sections 4 and 8.1 – Add “Each lot of Pregnyl® will be tested for EGF content prior to administration so that the precise EGF dose administered is known.” • Schema, sections 4, 7.1, 7.2, 10.1, 10.2, 11.2, 13.1- revise DLT assessment period to “occurring by day 21 after the 1st dose of Pregnyl®”, previously was day 7 for males and day 14 for females • Sections 7.1, 7.2 and 7.4 – remove individual dose level reductions due to DLTs • Section 10.3 – delete reference to patients receiving supplement as now such patients are excluded • Section 13.1 – expand CRM section for clarity • Section 13.4 – recalculated early study stopping rule by lowering the expected toxicity rate • Section 15 – update reference 22 from abstract to full publication 	Parent
	08/14/2015	
A complete response to the FDA's deficiency request (dated 08/13/2015):
 
 • Synopsis, Sections 5.1, 10.1 and 10.2, appendix 1 – add baseline eGRF and LVEF requirements for eligibility • Synopsis, Section 5.2 and appendix 1 - expand exclusion criteria to exclude patients with a hormone responsive malignancy, an active or recent thrombus (irrespective of anticoagulation status) • Need to correct reference 	yes
	09/12/2016	Section 5.1 Clarification of inclusion/exclusion criteria, expansion to include patients with steroid-dependent aGVHD, late-onset aGVHD, and overlap syndrome	
	11/30/2016	Section 5 , Clarification of eligibility criteria, evaluability, patient replacement, and Appendix 1	No
	03/22/2017	Corrected typo in Section 6.4 in response to CPRC stipulations on version 11/30/16	No
	06/21/2017	Section 5 , Updated eligibility to include patients from 0-12 Section 7.1 and Section 7.2 , Separated Arm 2 into Arm 2A (steroid-dependent) and 2B (steroid-refractory), and expanded dosing cohorts for Arm 2B given preliminary laboratory analyses.	Yes
	10/28/2017	Section 13 , Edited the statistical section due to CPRC stipulations on 6/21/17 amendment	
	05/17/2018	Fixed typographical error in study schema dose levels; Section 5 , updated eligibility based upon biomarkers	no

12	Study Data Collection and Monitoring.....	39
12.1	Data Management	39
12.2	Case Report Forms.....	39
12.3	Data and Safety Monitoring Plan (DSMP)	39
12.4	IND Annual Reports	40
12.5	Monitoring	40
12.6	Teleconferences – Lead Site and Affiliate Site	40
12.7	Affiliate Site Monitoring	40
12.8	Record Retention.....	41
13	Statistical Considerations	41
13.1	Study Design	41
13.2	Sample Size Consideration.....	46
13.3	Statistical Analysis	47
13.4	Early Stopping Rule	48
14	Conduct of the Study	48
14.1	Good Clinical Practice.....	48
14.2	Ethical Considerations	48
14.3	Informed Consent	48
15	References.....	49

Protocol Synopsis

Study Design: This multi-center center phase I/II study will use Continual Reassessment Method (CRM) to establish a maximum tolerated dose (MTD) of human chorionic gonadotropin and epidermal growth factor supplementation (hCG) as an adjunct to facilitate mucosal healing and immune tolerance in conjunction with accepted, standard immunosuppressive therapy in the setting of high-risk (Arm 1) and steroid-dependent (Arm 2A) and steroid-refractory (Arm 2B) acute graft-versus-host disease (aGVHD). Enrollment and dose escalation of Pregnyl® will be independent for each arm.

After completion of the dose finding trial for each arm, the final doses will be carried forward into a two-stage phase II extension trial to confirm safety and make a preliminary determination of the activity level for Arm 1, Arm 2A and Arm 2B. If the phase I trial enrolls fewer than 13 patients at the MTD, we will employ Simon's Minmax two-stage design with the possibility to discontinue after the 1st stage if the response rate is low.

- Stage 1: Enroll a total of 12 patients (including all treated at the MTD in phase I). If 5 or more of these respond, the trial will continue to stage 2.
- Stage 2: Enroll an additional 14 patients. If 14 or more out of 26 patients respond, hCG will be considered promising for further investigation.

If phase I trial enrolls more than 12 patients at the MTD, we will adjust the futility rule above for the two stage design with the giving number of patients enrolled at the MTD.

Primary Objective: **Phase I:** To determine the maximum tolerated dose (MTD) of Pregnyl® when given in combination with standard immunosuppressive therapy in pediatric and adult patients with high-risk (Arm 1) or steroid-refractory/dependent (Arm 2) aGVHD

Phase II: To determine the proportions of complete, partial, mixed, and no response among surviving patients at days 28 after initiation of protocol therapy in pediatric and adult patients with high-risk (Arm 1) or steroid-refractory/dependent (Arm 2) aGVHD

Secondary Objectives:

- To determine the safety and feasibility of hCG supplementation with Pregnyl® in combination with standard immunosuppressive therapy in pediatric and adult patients with high-risk or refractory aGVHD
- To determine the incidence of acute GVHD flare after CR/PR requiring increase of steroids or other systemic treatment at days 28 and 56
- To compare the rate of treatment failure for acute GVHD at days 28 and 56 after initiation of protocol therapy to historical controls

Transplant Related Objectives:

- Disease-free survival, overall survival, and non-relapse mortality at day 28, 56, 180 and 1 year of protocol treatment
- Incidence of chronic GVHD at day 180 and 1 year

Correlative Objectives:

- Pharmacokinetics (clearance, half-life, volume of distribution) of the both the hCG and EGF components of urinary hCG when administered to patients with GVHD
- Monitoring for hormonal effects via determination of serum concentrations of hCG, estradiol, progesterone, and testosterone on days 7, 14, 28, and 56, compared to baseline
- Collection of blood samples for measurement of immune and tissue damage/repair biomarkers to determine change from pre-treatment levels to levels obtained on days 7, 14, 28, and 56 post-treatment
- Analysis of previously collected skin and/or gastrointestinal biopsies for biomarkers of refractory aGVHD and response to therapy

Patient Population: HCT recipients 0 to 76 years of age within the first 7 days of initial treatment of high-risk (Arm 1) or steroid-refractory (Arm 2) aGVHD at any time in their treatment course

[figure not shown]
Inclusion Criteria: Renal: Serum creatinine $\leq 2.5 \times$ upper limit of normal (ULN)
Cardiac: Left ventricular ejection fraction (LVEF) $\geq 35\%$

Exclusion Criteria:

- Progressive malignancy
- Uncontrolled infection at initiation of protocol treatment
- Unwilling or unable to stop supplemental sex hormone therapy (estrogen, progesterone, and/or testosterone preparations)
- Diagnosis of a hormone responsive malignancy
- Current thromboembolic disease requiring full-dose anticoagulation - patients receiving pharmacologic prophylaxis for thromboembolic disease will be eligible
- Active or recent (within prior 3 months) thrombus, irrespective of anticoagulation status
- Pregnancy
- Women or men of childbearing potential unwilling to take adequate precautions to avoid unintended pregnancy from the start of protocol treatment through 28 days after the last treatment

Enrollment Plan: Phase I: Up to 20 patients in each arm with an estimated 2 years to accrue patients
Phase II component (for each arm):
Stage 1: Enroll a total of 12 patients (including all treated at the MTD in phase I). If 5 or more of these respond, the trial will continue to stage 2.

Stage 2: Enroll an additional 14 patients. If 14 or more out of 26 patients respond, hCG will be considered promising for further investigation.

***NOTE: Arm 2B, dose level 5: to avoid using vials from more than one Lot of study product, the maximum dose is either (1) the contents of a single 10,000 IU vial, or (2) a maximum dose of 10,000 IU from multiple vials. All vials used should be from the same Lot.**

Arm 1, Arm 2A and Arm 2B will be treated as separate, independent cohorts. Each lot of Pregnyl® will be tested for EGF content prior to administration so that the precise EGF dose administered is known.

Phase I:

For each arm, dose levels of Pregnyl® will be tested starting at dose level 1. Dose levels -1 and -2 will be used only if dose level 1 proves too toxic.

The 1st 2 patients will be enrolled in dose level 1. The next cohort of 2 patients will not begin treatment until all patients in the current cohort have reached day 21. Each new cohort of 2 patients will be assigned by the study statistician to the most appropriate dose level based on toxicity probabilities set for this study. The MTD for each arm (high-risk and steroid-refractory aGVHD) will be identified at or before the total sample size of 20 patients per arm is reached.

The dose limiting toxicity (DLT) is defined as any of the following occurring by day 21 after the 1st dose of Pregnyl®:

- In males and females: Grade 2-4 thromboembolic event (CTCAE v4) i.e., any thrombosis more severe than a superficial venous thrombosis where treatment is required
- In males and females: Grade 3-4 ascites (CTCAE v4)
- Specific to females: Ovarian hyperstimulation syndrome, defined as the rapid development of enlarged, cystic, painful ovaries

Phase II Extension:

- **Stage 1:** Enroll a total of 12 patients (including all treated at the MTD in phase I). *If 5 or more of these respond, the trial will continue to stage 2.*
- **Stage 2:** Enroll an additional 14 patients. *If 14 or more out of 26 patients respond, hCG will be considered promising for further investigation.*

1 Study Objectives

1.1 Primary Objective

Phase I: To determine the maximum tolerated dose (MTD) of Pregnyl® when given with standard immunosuppressive therapy in pediatric and adult patients with high-risk or refractory acute graft-versus-host disease (aGVHD).

Phase II: To determine the proportions of complete, partial, mixed, and no response among surviving patients at days 28 after initiation of protocol therapy in pediatric and adult patients with high-risk (Arm 1) or refractory (Arm 2) aGVHD.

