- **Progression:** deterioration of any organ involved.

- **No Response (NR):** absence of any improvement or progression as defined above.

10 Schedule of Patient Activities

Scheduled evaluations after screening and through day 19 of the last treatment cycle may be performed +/-2 days from the targeted date; assessments performed after day 28 and through day 56 may be done +/-5 days of the targeted date. After day 56, assessments will coincide with the post-transplant follow-up schedule (i.e., additional clinic visits specifically for this study will not be required). In addition, targeted days may be altered as clinically appropriate, and will not constitute a protocol deviation.

Schedule of Treatment, Tests and Procedures – Arm 1

	Baseline	Treatment Days +/- 2 days												Phase I only	Follow Up +/- 5 days***	
Procedures, evaluations, and treatment		1	3	5	7	9	11	13	14	15	17	19		21	28	56
Standard of Care																
Vital signs and weight	X	X	X	X	X	X	X	X	X	X	X	X			X	X
Performance status (Karnofsky or Lansky)	X				X				X			X			X	X
Acute GVHD staging	X				X				X						X	X
Complete blood count	X				X				X			X			X	X
Complete metabolic panel	X				X				X			X			X	X
Serum creatinine	X															
Ejection Fraction by echocardiogram or MUGA	X															
Research																
Pregnyl® dosing*		X	X	X	X	*										
Assess for toxicity		beginning with the 1st dose of Pregnyl® and continuing for 4 weeks after the last dose per section 11.2 (if phase I assess for DLT at day 21)														
Pharmacokinetics**		X			X											
Serum hCG	X^				X				X						X	X
Estradiol, progesterone, and testosterone	X				X				X						X	X
Collection of blood samples for immune and tissue damage/repair biomarkers (refer to section 10.3 for blood volume and tube type)s	X				X				X						X	X

MT2014-12: hCG supplementation in high-risk or refractory aGVHD

Research related blood samples will go to Translational Therapy Lab (TTL) for processing and storage until study related testing.

*If a patient achieves a complete or partial response, he/she may continue to receive maintenance Pregnyl® doses twice per week, in the dose level he or she was already assigned, for another 10 doses, beginning during protocol day 9-12.

**Blood samples (2 ml plasma) collected 30 (\pm 10) minutes pre-dose, and at post-dose 1 hour (\pm 5 min), 3 hours (\pm 5 min), 6 hours (\pm 10 min), and 24 hours (\pm 30 min).

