13.1 Study Design

This is a multi-center phase I/II study of supplemental hCG as an adjunct to facilitate improved mucosal healing and immune tolerance in conjunction with accepted, standard immunosuppressive therapy in the setting of high-risk (Arm 1), steroid-dependent (Arm 2A) aGVHD and steroid-refractory (Arm 2B). Once the MTD is identified, the objective will be to confirm safety and obtain preliminary estimates of the primary trial endpoint defined as complete response (CR) and partial response (PR) at day 28.

Phase I component: Estimating the MTD of hCG for Arm 1 and Arm 2A

The first phase is a dose finding study. The dose escalation will be two independent processes with CRM for Arm 1 (high-risk aGVHD) and Arm 2A (steroid-dependent aGVHD). The target toxicity rate was determined based on clinical input and acceptability. Continual reassessment method (CRM)

is originally proposed by O'Quigley et al [31]. The goal for CRM is to identify the dose level which corresponds to the desired toxicity rate of 25% or less. We are choosing a lower target toxicity than would be chosen under the standard design. A standard “3+3” design will often choose a dose with corresponding to a toxicity rate of 33% or lower. The trial will stop if the posterior probability (that the lowest dose is more toxic than the target dose) is 0.90.

Dose Level	hCG Dose
-2**	125 USP hCG/875 pg EGF/m ²
-1*	250 USP hCG/1,750 pg EGF/m ²
1	500 USP hCG/3,500 pg EGF/m ²
2	1,000 USP hCG/7,000 pg EGF/m ²
3	2,000 USP hCG/14,000 pg EGF/m ²

*Dose level -1 (250 USP hCG/1,750 pg EGF/m²) will be used only if Dose Level 1 (500 USP hCG/3,500 pg EGF/m²) proves too toxic.

**Dose level -2 (125 USP hCG/875 pg EGF/m²) will be used only if Dose Level -1 (250 USP hCG/1,750 pg EGF/m²) proves too toxic.

Initial estimates of toxicity or the “skeleton” estimates are given by the clinicians. The estimates of toxicity for Arm 1 and Arm2 are listed as 1%, 2%, 5%, 10% and 20% for the 5 dose levels, respectively. The 1st 2 patients will be enrolled in dose level 1.

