Dose	Actual probability in theory of having a DLT at each dose	Probability of Selecting the specified dose given the probabilities of having a DLT listed in the 2nd column	Estimated Number of subjects treated at each dose level during the study
125 USP hCG/875 pg EGF/m ²	0.25	0.28	6.7
250 USP hCG/1,750 pg EGF/m ²	0.30	0.29	3.1
500 USP hCG/3,500 pg EGF/m ²	0.40	0.23	5.3
1,000 USP hCG/7,000 pg EGF/m ²	0.50	0.07	2.6
2,000 USP hCG/14,000 pg EGF/m ²	0.60	0.02	0.7
3,500 USP hCG/24,500 pg EGF/m ²	0.70	0.00	0.2
5,000 USP hCG/35,000 pg EGF/m ²	0.75	0.00	0.1

Phase II extension: Studying the efficacy of hCG (Arm 1, Arm 2A and Arm 2B)

After completion of the dose finding trial for each arm, the final doses will be carried forward into a two-stage phase II extension trial to confirm safety and make a preliminary determination of the activity level for Arm 1 and Arm 2. If the phase I trial enrolls fewer than 13 patients at the MTD, we will employ Simon’s Minmax two-stage design (Simon, 1989) with the possibility to discontinue after the 1st stage if the response rate is low.

- **Stage 1:** Enroll a total of 12 patients (including all treated at the MTD in phase I). *If 5 or more of these respond, the trial will continue to stage 2.*

- **Stage 2:** Enroll an additional 14 patients. *If 14 or more out of 26 patients respond, hCG will be considered promising for further investigation.*

If phase I trial enrolls more than 12 patients at the MTD, we will adjust the futility rule above for the two stage design with the giving number of patients enrolled at the MTD.

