13.2 Sample Size Consideration

Resulting from laboratory studies conducted on the first several patients on this study, the investigative team plans to test higher doses in steroid-refractory patients with aGVHD (separating of Arms into 2A and 2B). This necessitates expanding the number of participants treated on the arms as described below:

Arm 1 Treated Patients	Arm 2A Treated Patients	Arm 2B Treated Patients
Level 1: N = 2, DLT = 0	Level 1: N = 1, DLT = 0	Level 1: N = 1, DLT = 0
Level 2: N = 2, DLT = 0	Level 2: N = 0, DLT = 0	Level 2: N = 2, DLT = 0
Level 3: N = 6, DLT = 0	Level 3: N = 3, DLT = 0	Level 3: N = 4, DLT = 0
Enroll 10 more patients Next dose level 3: N = 2	Enroll 16 more patients Next dose level 3: N = 2	Enroll 13 more patients Next dose level 4: N = 2

- The next dose was calculated with R package “dfcrm”.
- The next dose for Arm 2B was dose level 5, but restrict the dose jump, so the next dose will be dose level 4.

We now anticipate recruitment of 20 participants in each of the 3 arms to complete phase I.

In phase I, based on resources, the maximum number of allowable evaluable patients is 20 for each arm (total of 60 for all three arms). The simulations show it should be sufficient and safe to define the MTD for future efficacy trials.

For Arm 1 or 2A, if fewer than 13 patients are enrolled at the MTD, the phase II extension trial using Simon's two-stage Minmax design will require 26 patients to test the null hypothesis that the response rate at day 28 is <40% versus the alternative that the response rate is $\geq 65\%$ after assuming 80% power and a significance level of 0.05 and using a maximum of 26 patients. We will choose the rule that minimizes the expected sample size giving a true response rate equivalent to the null hypothesis. We expect that for each arm, phase I and II will require approximately 33 patients due to use of patients from the phase I trial in the phase II extension ([table 2](#) shows about 13 patients will be treated under MTD). But the sample size for each

arm could be as high as 44 when only two patients were treated at MTD in phase I. Therefore we expect the sample size of the phase I/II study for Arm 1 and Arm 2A will be 66 to 88 patients.

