13.3 Statistical Analysis

SAS 9.3 (Cary, NC, USA) will be used for the statistical analyses. For binary endpoints such as toxicity, summary statistics including proportions and their 95% confidence intervals will be calculated for each arm. All toxicity and safety assessments will be presented in the data listings and summarized with descriptive statistics. Response at day 28 will be estimate with simple proportions and descriptive plots.

The secondary endpoint, proportions of response among the surviving patients at day 7, 14, 56 and 180, treatment failure proportion for acute GVHD at day 28, 56 and 180 after initiation of protocol therapy, the incidence of acute GVHD flare after CR/PR requiring increase of steroids or other systemic treatment at days 28, 56, and 180 will be estimated. Overall survival and disease free survival probabilities after the initial treatment will be estimated using Kaplan-Meier's method. Treatment-related mortality and the incidence of chronic GVHD after the initial treatment will be estimated by competing risk analysis. For other correlative endpoints, continuous measures will be summarized with mean and SD for each arm and time point (if skewed, we will report median and interquatile range) and categorical measures will be summarized with frequency and percentage.

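### The phase II primary response proportion is restricted to day-28 survivors in the synopsis and 1.1, but sections 13.1 and 13.2 judge CR+PR out of all 12 and 26 counted patients

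*Combined protocol and SAP*

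**What the plan says.** The synopsis and section 1.1 both restrict the phase II primary proportions to patients alive at day 28. Section 1.1 reads "To determine the proportions of complete, partial, mixed, and no response among surviving patients at days 28 after initiation of protocol therapy".

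Section 13.1 describes the "primary trial endpoint defined as complete response (CR) and partial response (PR) at day 28", with no survival condition. Its decision rule is a count out of a fixed number: at least 5 responders of 12 to continue, and then "If 14 or more out of 26 patients respond, hCG will be considered promising for further investigation". Section 13.2 sizes each arm on the same basis. The extension "will require 26 patients to test the null hypothesis that the response rate at day 28 is <40"%, against an alternative of at least 65%.

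Section 13.3 says only this for day 28: "Response at day 28 will be estimate with simple proportions and descriptive plots". For the secondary time points it does name survivors: "proportions of response among the surviving patients at day 7, 14, 56 and 180".

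Section 9 defines CR, PR, mixed response, progression and no response by organ stage. No response is the "absence of any improvement or progression as defined above". None of the categories mentions death.

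Section 6.4 makes a phase II patient assessable for response after 3 doses in Arm 1 or 6 doses in Arms 2A and 2B, and replaces patients who fall short. It does not mention death.

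**The concern.** One primary endpoint has two denominators. A patient who dies before day 28 cannot be a day-28 responder, so leaving the deaths out removes only non-responders. The survivor-only proportion is therefore higher than the proportion of all counted patients whenever there is at least one death and one responder.

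An arm could then fail its decision rule while its reported primary proportion lies above the proportion that would have passed. The plan does not say which figure is the primary result, so the choice could be made after the deaths are known. Deaths are foreseeable: section 3 describes these conditions as often fatal.

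**Working it through.** **Inputs.** Stage sizes 12 and 26 and cutoffs 5 and 14 (13.1). Rates of 40% and 65%, significance level 0.05 and power 80% (13.2). The documents give no day-28 mortality *d*, so values from 2% to 20% are assumed.

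**Step 1. The plan's sample size.** An exact search for the minimax two-stage design (40% versus 65%, one-sided 0.05, power 80%) returns a maximum of 26 with 12 in stage 1, as stated. The printed cutoffs (5/12 and 14/26) give a false-positive rate of 10.4% and power of 90.7%. The minimax cutoffs would be 6/12 and 15/26 (4.7% and 80.9%). That difference is a separate matter. The figures below use the printed rule.

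**Step 2. When the two denominators disagree.** With R responders and D deaths among 26, the arm fails if R ≤ 13, but the survivor proportion R/(26 − D) exceeds 14/26 = 53.8% once D is large enough.

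| R | Of all 26 | Fewest deaths needed | Of survivors |
|---|---|---|---|
| 13 | 13/26 = 50.0% | 2 | 13/24 = 54.2% |
| 12 | 12/26 = 46.2% | 4 | 12/22 = 54.5% |
| 11 | 11/26 = 42.3% | 6 | 11/20 = 55.0% |

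**Step 3. Average shift.** If 40% of all counted patients respond, the survivor-only rate is 0.40/(1 − d): 42.1%, 44.4%, 47.1% and 50.0% at d = 5%, 10%, 15% and 20%.

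**Step 4. How often the reported figure contradicts the rule.** Each patient independently responds (probability p), is dead by day 28 (d), or neither. Sum over stage 1 responders ≥ 5 of 12 and total R ≤ 13 of 26, with D given R binomial (26 − R, d/(1 − p)), and keep the outcomes where R/(26 − D) > 14/26.

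| Assumed d | 2% | 5% | 10% | 15% | 20% |
|---|---|---|---|---|---|
| p = 40% (null) | 0.6% | 2.6% | 7.6% | 13.6% | 20.3% |
| p = 65% (alternative) | 0.7% | 2.5% | 5.0% | 6.2% | 6.6% |

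The second row levels off because few arms reach 26 and fail at 65%. Stage 1 stopping has probability 0.0255 and success 0.9073, which leaves 1 − 0.0255 − 0.9073 = 6.7%. At 40% the same remainder is 1 − 0.4382 − 0.1039 = 45.8%.

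**Step 5. Deaths before the minimum dose count (conditional on how 6.4 is read).** The 3rd dose is scheduled on day 5 and the 6th on day 11. Let e be the assumed share of patients who die before then.

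- If 40%/65% describe all treated patients and these deaths are replaced, the null rate among counted patients becomes 0.40/(1 − e). That is 40.8% at e = 2% and 42.1% at e = 5%. The printed rule's false-positive rate moves from 10.4% to 12.0% or 14.9%.
- If 40%/65% describe dose-evaluable patients, replacement causes no inflation. Counting these deaths as failures instead makes the alternative 0.65 × (1 − e), which is 63.7% or 61.75%. Power moves from 90.7% to 88.2% or 83.6%.

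**The case against.** The best defence is that section 13 already settles the decision. CR and PR are defined by organ stage, a dead patient can meet neither, and the rule is a fixed count, so such a death is a non-response in 14 of 26. Section 13.3 points the same way, since it names survivors at the other time points but not at day 28. On this view the phrase in 1.1 and the synopsis is a stray one. A reader of 13/24 can also still see that there were fewer than 14 responders, and no passage makes 53.8% a reporting threshold. Day-28 survival and non-relapse mortality are listed separately in 1.4.

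Most of this stands, and it limits the point. A reader might infer that deaths inflate the go/no-go decision. The text does not support that for deaths after the minimum doses. A reader might also take 6.4 to replace patients who die early. Its wording does not exclude this, but its clause on re-consenting suggests that living patients were meant. Nothing in the documents supports replacing every death before day 28.

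What does not fall away is that the restriction stands in the primary objective itself, in two places. The answer for deaths has to be inferred from section 9, and that inference conflicts with 1.1.

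**Conclusion.** The concern holds as a contradiction over the reported primary proportion. If 1.1 is followed, that proportion is biased upward and can sit above the passing proportion in an arm that failed. The decision rule itself is sound on this point.

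The size depends on a day-28 mortality that the documents do not give. At 2% to 5%, the contradiction in step 4 has a probability of 0.6% to 2.6% at either design rate. At 10% to 20%, it is 7.6% to 20.3% at a true rate of 40% and 5.0% to 6.6% at 65%. These figures assume independent patients and one common mortality.

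The treatment of early deaths under 6.4 is a conditional point. Whether replacement matters depends on whether 40% and 65% describe all treated or dose-evaluable patients, which the plan does not say. It should be corrected, and the correction is easy.

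**What to change.** - **Synopsis and 1.1:** delete the survivor restriction from the day-28 primary endpoint.
- **13.1 and 13.3:** state that the primary proportion is CR plus PR divided by all patients counted in the 12 and 26 (or in the adjusted counts if more than 12 are treated at the MTD), with death before day 28 counted as non-response.
- **Optional:** keep the survivor-only proportion as a descriptive figure, labelled as conditional on survival.
- **6.4 and 13.2:** state whether a patient who dies before the minimum dose count is replaced, and which population the 40% and 65% rates describe. Settle the two together, because the effect on error rates depends on both.

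The first two changes need only wording and no new data. Their cost is that reported day-28 rates may be a few points lower, as with 50.0% instead of 54.2% in the example. If the sponsor chooses to count early deaths as failures and the rates describe dose-evaluable patients, the power loss in step 5 is a further cost.
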